3.6.2. Multicenter Studies

Due to the large number of participating sites resulting in diminished sample sizes within each site, no adjustment or stratification for site will be performed. Data from all centers will be pooled for the primary analysis. By site/region analysis of the primary endpoint may be explored.

3.7. Changes to Protocol Specified Analysis

There are no changes in the protocol-specified analyses of efficacy (primary, secondary, and exploratory), safety, and PK endpoints. Exploratory analyses for the patient-reported outcomes and biomarkers will not be performed due to futility of the primary efficacy endpoint.

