8. STATISTICS

A SAP will be prepared and approved before the interim analysis to provide a more detailed description of the nature of the analyses and the manner in which results will be compiled. The SAP will include details of the statistical models to be used and the test statistics to be employed.

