8.4.5.2. Laboratory Abnormalities

The severity of laboratory abnormalities will be graded using the NCI CTCAE V5.0 whenever possible. The frequency of subjects experiencing a specific laboratory abnormality will be tabulated by treatment group and worst severity. In addition, the number and percentage of subjects experiencing a specific laboratory abnormality will be tabulated similarly.

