3.5. Interim Analysis

One interim analysis of the study's primary endpoint (PFS) was planned to be performed when approximately 36% of the PFS events occur (approximately 88 events). An O'Brien-Fleming spending function will be used to calculate the sequential HR boundaries based on the actual number of PFS events.

Assuming there are 88 events at this interim analysis, then the study may stop for efficacy if the observed HR is less than 0.447 or stop for futility if the observed HR is more than 0.67.

Based on the results of planned interim analysis, the Data Monitoring Committee recommended discontinuing the study due to futility.

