6.2. Laboratory Values

Laboratory values will be presented in standard units. For multiple values for a test at a visit from the same laboratory, the last non-missing value at that visit will be used.

Mean and mean change from baseline in clinical laboratory data will be summarized at each scheduled nominal visit by treatment group.

In addition, box plot of hematology and chemistry parameters will be presented by nominal visit and treatment group.

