10. REVISION HISTORY

Version Number	Date	Description
1.0	25 July 2024	Initial release

PTC596-ONC-008-LMS

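### SAP 3.7 declares the efficacy and safety analyses unchanged, yet three differ from the protocol, the log-rank test is no longer named, and the only listed SAP version follows the interim outcome

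*SAP*

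**What the plan says.** Protocol section 8 (Statistics) sets the order of events: "A SAP will be prepared and approved before the interim analysis". The SAP's revision history (section 10) lists one version, 1.0, dated 25 July 2024 and described as "Initial release". Section 3.5 of that same version reports that "the Data Monitoring Committee recommended discontinuing the study due to futility".

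On content, SAP 3.7 says: "There are no changes in the protocol-specified analyses of efficacy (primary, secondary, and exploratory), safety, and PK endpoints". The next sentence discloses one change: the exploratory patient-reported-outcome and biomarker analyses are dropped because of futility.

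On laboratory safety, protocol 8.4.5.2 says: "The severity of laboratory abnormalities will be graded using the NCI CTCAE V5.0 whenever possible". It then calls for frequencies by treatment group and worst severity. SAP 6.2 says instead: "Mean and mean change from baseline in clinical laboratory data will be summarized at each scheduled nominal visit by treatment group". It adds box plots and mentions no grading.

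**The concern.** A section on changes from the protocol tells the reader which analyses were fixed in advance and which were not. Here it says that none of the efficacy, safety or PK analyses changed, and a comparison of the two documents shows otherwise. SAP section 1 promises that deviations from the SAP will be documented in the study report. A departure from the protocol that is written into the SAP is not a deviation from the SAP, so 3.7 is the natural place to disclose it.

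Timing adds to this. Because version 1.0 followed the interim outcome, a reader who trusts 3.7 will take every analysis in it as settled beforehand.

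The laboratory change bears on safety. Protocol 1.3 reports that the most common treatment-related Grade 3 or 4 events in the Phase 1b study were associated with myelosuppression. A visit-by-visit mean can look unremarkable while a minority of subjects have severe cytopenia. A worst-grade table is designed to show those subjects.

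**Working it through.** The point concerns consistency and sequence, so the check is a side-by-side reading.

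**The plan's own interim figures.** These are not in dispute, and they reproduce. The information fraction is t = 88/245 = 0.3592. O'Brien-Fleming-type spending gives 2 × [1 − Φ(2.2414/√0.3592)] = 0.000184, with z = 3.562. Under 2:1 allocation the efficacy boundary is exp(−3.562/√(88 × 2/9)) = exp(−3.562/4.422) = 0.447. Both match protocol 8.2.

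**Same base version.** SAP section 1 cites protocol version 4.0 of 28 November 2023, the version compared here. The differences are therefore not left over from an older protocol.

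**Protocol against SAP**

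- *ORR and DCR difference.* Protocol 8.4.4 specifies CMH methodology adjusted for the PFS stratification factors, and analyses DCR in the same way as ORR. SAP 5.3.1.2 and 5.3.1.3 give a between-arm difference with a Wald 95% interval and state no stratification. With three binary factors, the protocol estimate combines 2 × 2 × 2 = 8 strata; the SAP estimate, as written, combines none. This is a different estimator.
- *PFS landmarks.* Protocol 8.4.2: {3, 6, 12, 18, 24, 30} months. SAP 5.1.1: {2, 4, 6, 8}. The intersection is {6}, so five of the six protocol times are dropped and three of the SAP's four are new.
- *Laboratory safety.* Protocol 8.4.5 and 8.4.5.2 specify worst-grade CTCAE summaries. SAP 6.2 specifies means, mean changes and box plots by nominal visit. The graded tabulation is not carried over.
- *PFS p-value.* Protocol 8.4.2 names a stratified log-rank test, with the stratified Cox model supplying the hazard ratio and its interval. SAP 5.1.1 takes the hazard ratio, p-value and interval from a stratified Cox model. It names neither the log-rank test nor the type of Cox test.

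**Do the adverse event tables replace the graded laboratory tables?** SAP 6.1 keeps events by maximum severity and at Grade 3 or higher. Protocol 7.3.1, however, keeps laboratory abnormalities out of AE reporting when they prompt neither treatment nor further work-up. An asymptomatic graded cytopenia that led to no action would appear only in a laboratory table. SAP 3.1 also excludes unscheduled-visit data from summary tables, so visit means can miss values taken between scheduled draws.

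**Sequence.** The documents do not date the interim. Version 1.0 reports the resulting recommendation, so that version was released after the outcome was known. No earlier version is listed.

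**The case against.** Much can be said for the sponsor.

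- *3.7 is not a blanket denial.* It openly drops the patient-reported-outcome and biomarker analyses. The inaccuracy is confined to efficacy and safety.
- *A SAP may add detail.* The protocol says so: "A SAP will be prepared and approved before the interim analysis to provide a more detailed description". The rule removing strata with fewer than 5 subjects in an arm (SAP 5.1.1) and sensitivity analyses (c) and (d) (SAP 5.1.2) replace nothing in protocol section 8. They do not contradict 3.7 and matter here only for their timing.
- *The primary test may not have changed.* If the factors enter as strata and treatment is the only covariate, the score test from the Cox model is the stratified log-rank test apart from tie handling. A reader might infer that the primary test was swapped; the text supports only an ambiguity.
- *The landmarks are descriptive.* After an early stop, late Kaplan-Meier estimates may not be supportable. That is a good reason to change them, but 3.7 does not give it.
- *Clinically acted-on myelosuppression still appears by grade* in the AE tables. The table shells are in a separate document that was not supplied, so graded laboratory tables may exist there. The SAP text still does not specify them.
- *The interim had its own documents.* The protocol assigns its conduct to a DMC Charter and a DMC SAP, also not supplied. These may have fixed the interim analysis in advance. They would not settle the other analyses in version 1.0.
- *The SAP does not hide its chronology.* It gives its own date and the futility recommendation. With the trial stopping for futility, a false efficacy claim is not the main risk.

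These arguments narrow the point. They do not make the 3.7 sentence correct.

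**Conclusion.** The point holds as a correction to the SAP that also changes some reported results. Its size is three clear departures from protocol section 8 (the ORR/DCR difference, the PFS landmarks and the laboratory grading) and one ambiguity (the source of the PFS p-value). Three further items, namely the small-strata rule and sensitivity analyses (c) and (d), should carry a timing label. No numerical effect can be given without data.

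A reader might infer that the choices in version 1.0 were selected on unblinded data. The documents do not support that. Protocol 3.1 has an external vendor perform the interim for the DMC, and protocol 5.6 keeps sponsor staff blinded until the primary analysis, apart from pharmacovigilance staff for expedited safety reporting. What is established is that version 1.0 was released after the interim outcome was known. When each choice was made, and what the authors had seen, is not recorded.

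The conclusion assumes that the revision history is complete and that no separate document restores the missing analyses.

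**What to change.** 1. In SAP 5.3.1.2 and 5.3.1.3, restore the stratified CMH difference and its interval for ORR and DCR.
2. In SAP 6.2, restore laboratory abnormalities by worst CTCAE grade and treatment group. State that unscheduled values count, since SAP 3.1 would otherwise remove them.
3. In SAP 5.1.1, name the stratified log-rank test as the source of the PFS p-value and keep the stratified Cox model for the hazard ratio and interval.
4. Rewrite SAP 3.7 after a line-by-line comparison with protocol section 8. List each remaining departure, including the landmarks, with its reason. State that version 1.0 followed the interim outcome and whether its authors were blinded, and cite the DMC SAP by version and date.
5. Label the small-strata rule and sensitivity analyses (c) and (d) as first specified after the interim outcome was known, without implying that they were data-driven. Carry the same wording into the study report.

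The cost is revised SAP and report text and a few standard tables. The comparison found no need for new data collection.

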4. PATIENT DATA

4.1. Patient Disposition

The following subject disposition information will be provided:

- Number of screenings.
- Number of unique subjects screened.
- Number of subjects in the ITT, mITT, and safety analysis set
- Number who have discontinued treatment.
- The primary reason for treatment discontinuation

A listing of these data will also be provided.

4.2. Data Sets Analyzed

A summary of the number of subjects for each analysis dataset will be provided.

4.3. Demographics and Baseline Characteristics

Demographics and baseline characteristics including age, age group (18-64 years, 65-84 years, 85 years and over), sex, race, ethnicity, height, weight, body surface area (BSA), body mass index, region, and time since initial diagnosis will be summarized by treatment group and overall, for the safety analysis set. Stratification factors (prior lines of therapy, ECOG, histological tumor type) will also be summarized.

4.4. Disease Characteristics

Disease characteristics include histological tumor type (see above), measurable disease status per RECIST 1.1 criteria, disease stage at study entry, and time from initial diagnosis.

Demographic and baseline characteristic data, including disease characteristics, will be listed by subject.

4.5. Medical History

Subject medical history will be coded using the Medical Dictionary for Regulatory Activities (MedDRA) (Version 25 or higher) coding dictionary. A summary table by system organ class (SOC) and preferred term (PT) will be provided for each treatment group and overall. Subject medical history data will be listed by subject.

4.6. **Protocol Deviations**

Before database lock, protocol deviations will be documented separately in a stand-alone document that includes deviation category (e.g., violation of inclusion and exclusion criteria at screening, use of excluded concomitant medications, received the wrong treatment or incorrect dose), deviation description, CSR/non-CSR reportable, and visit/time point for each deviation).

CSR-reportable protocol deviations include those related to inclusion/exclusion criteria, conduct of the trial, subject management or subject assessment that impact the safety of the subjects or

jeopardize the quality of the study data. CSR-reportable protocol deviations are equivalent to a major protocol deviation.

CSR-reportable protocol deviations will be summarized. A subject listing of CSR-reportable protocol deviations will be provided for the safety analysis set.

4.7. Prior and Concomitant Medications

All investigator terms for medications recorded on the electronic case report form (eCRF) will be coded using the World Health Organization Drug Dictionary (version WHODrug-Global-B3 Sep 2021 or later).

Prior medications will be defined as medications started prior to the first dose of study drug. Concomitant medications will be defined as medications (other than the study drug) that either (1) started before the first dose of study drug and were continuing at the time of the first dose of study drug, or (2) started on or after the date of the first dose and within 30 days after last dose of study drug. Any medication started before the first dose of study drug and continued at the time of first dose will be considered as both prior and concomitant.

Any medication with partial or missing start date in which the prior medication status cannot be determined will be considered as a prior medication. Similarly, any medication with partial or missing end date in which the concomitant medication status cannot be determined will be considered as a concomitant medication.

Prior medication and concomitant medication will be summarized by treatment group as following for safety analysis set as:

• Number and percentage of subjects with at least one prior/concomitant medication.

By Anatomical Therapeutic Chemical level 2 and PT.

A subject data listing of all prior and concomitant medications will be provided.

Study Phase	Definition
Prior	End date < Study treatment start date
Prior and concomitant	Start date < Study treatment start date and were continuing at the time of the first dose of study drug
Post-treatment	Start date > Study treatment stop date + 30 days
Concomitant	If the medication is not prior nor post-treatment

 Table 2:
 Study Phases for Concomitant Medications

4.8. Extent of Exposure

The following will be summarized: duration of exposure for unesbulin/placebo and DTIC, number of unesbulin/placebo cycles completed, and number of unesbulin/placebo doses received.

Duration of exposure (days) is defined as

```
Last dose date (unesbulin/placebo) - First dose date + 1.
```

For unesbulin/placebo, last dose date is the dose date that recorded in the diary eCRF and/or End of treatment eCRF. Subjects known to be still on treatment after the data cut-off date will have the last dose date imputed as the data cut-off date.

The same calculation will be used to compute the duration of DTIC exposure. For DTIC, the last dose date is the dose date recorded in the DTIC administration eCRF and/or End of treatment eCRF. Subjects known to be still on treatment after the data cut-off date will have the last dose date imputed as the data cut-off date.

Duration of exposure and number of doses will be summarized by treatment group and overall for the safety analysis set.

By-subject listings will also be provided.

4.9. Treatment Modifications

The following will be summarized by treatment group for unesbulin/placebo and DTIC.

- Number of subjects with missed doses / reasons of missed doses
- Number of subjects with reduced doses / reasons for dose reductions.
- Infusion interruptions (DTIC) / reasons for infusion interruptions

A by-subject listing will also be provided.

5. EFFICACY ANALYSIS

The efficacy endpoint will be analyzed.

• PFS per ICR

Other efficacy endpoints (listed below) will be analyzed.

- OS
- ORR
- Disease control rate (DCR) or clinical benefit rate (CBR)
- Duration of response (DOR)

Tabular summaries for efficacy endpoints will be provided for the following analysis populations:

- The mITT population (the primary analysis population),
- The ITT population (sensitivity analysis)
- Subset of the ITT population with 4 or more prior line therapy (sensitivity analysis)
- By histological tumor type (Uterine and non-uterine) for the mITT population (subgroup analysis)
- Baseline ECOG PS score (0 and 1) for the mITT population (subgroup analysis)
- Prior lines of therapy (1 and >1) for the mITT population (subgroup analysis)
- Prior lines of therapy (4 or more) for the non-mITT population (subgroup analysis)
- Histologic tumor type in combination with number of prior lines of therapy (uterine with 1 prior line; uterine with 2-3 prior lines, non-uterine with 1 prior line; non-uterine with 2-3 prior lines) for the mITT population (subgroup analysis)

By-subject listings will also be provided.

5.1. Primary Analyses

5.1.1. **Progression Free Survival (PFS)**

PFS will be analyzed twice during the study: at the interim analysis, when approximately 88 events have occurred and at final analysis after 245 events have occurred. PFS is defined as the time from randomization to documented disease progression or death due from any cause, whichever occurs first. Subjects who are alive and have not progressed at the time of the analysis will be censored at the time of their last tumor assessment that was a CR, PR, SD, or non-CR/non-PD. Details of the censoring scheme for this endpoint are described in Table 3.

PFS will be analyzed using Kaplan-Meier (KM) methods. A summary table of the number of events, the number of censors, and KM estimates (25th, 50th, 75th percentile of PFS along with the 95% CI, and PFS probability at 2, 4, 6, 8 months, respectively) will be provided by treatment.

KM curve of PFS will be provided using the mITT and ITT populations.

The HR, p-value and 95% CI will be estimated using a stratified Cox proportional hazards regression model controlling for study stratification factors include prior lines of therapy (1 versus

>1), ECOG PS score (0 versus 1), and LMS origin (uterine versus nonuterine). If there are stratification errors (eg, a subject with ECOG score=1 randomized in the ECOG score=0), this analysis will be stratified by the planned strata in the study randomization scheme (ie, stratification errors will be ignored). However, a sensitivity analysis with PFS stratified by actual strata will be performed. A listing showing planned and actual randomization strata will also be provided. Strata with less than 5 subjects in any given treatment arm will not be included (ie, when there are less than 5 subjects in the ECOG =1 for the placebo group then ECOG stratum will be eliminated from the model).

Scenario	Date of Event/Censoring	Outcome
No post-baseline response assessments and no death or PD	Date of randomization	Censored
No PD and no death	Date of last adequate response assessment	Censored
New anti-cancer treatment started before first PD	Date of last adequate response assessment prior to date of new anticancer treatment	Censored
New anticancer treatment taken but did not have PD/Death.	Date of last adequate response assessment prior to date of new anticancer treatment	Censored
New anti-cancer treatment taken after treatment starts but prior to the first response assessment	Date of randomization	Censored
PD	Date of PD If PD occurred within the timeframe of 2 consecutive scheduled scans ^a from the last adequate response assessment	Progressed
	Date of last adequate response assessment If the date of PD occurred after missing more than 2 consecutive scheduled scan assessments ^a	Censored
Death	Death date If death occurred within the timeframe of 2 consecutive scheduled scans ^a from the last adequate response assessment.	Progressed
	Death date If there are no post-baseline response assessments and death occurred within ≤14 weeks of the randomization date.	Progressed
	Date of randomization If there are no post-baseline response assessments and death occurred >14 weeks from the first dose.	Censored
	Date of last adequate response assessment If the date of death occurred after missing more than 2 consecutive scheduled scan assessments ^a	Censored

Table 3:	Censoring and Event Scheme for PFS
----------	------------------------------------

Abbreviations: PD, disease progression.

> 14 weeks (6+1+6+1=14) post last tumor assessment, if PD/death occurred within first 8 cycles (24 weeks) of treatment

> 17 weeks (6+1+9+1=17) post last tumor assessment, if subjects' PD/death occurs between cycle 8 and 14 (42 weeks) of treatment

> 20 weeks (9+1+9+1=20) post last tumor assessment, if subjects' PD/death occurs after cycle 14 (42 weeks) of treatment

^a 2 consecutive scheduled scan assessments are defined in weeks as follows:

The last adequate response assessment is defined as the date subject had an overall response of (CR, PR or SD or non-CR/non-PD)

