8.4.2. Analysis of Primary Efficacy Endpoints

The primary endpoint in this study is PFS. PFS is defined as the time from the randomization date to the date of the first documented tumor progression as determined by the independent, blinded radiologist using RECIST 1.1 or death due to any cause, whichever occurs first. Clinical deterioration in the absence of unequivocal evidence of progression (per RECIST 1.1) is not considered progression for purposes of determining PFS. Subjects who die without a reported prior progress or die will be censored on the date of their last evaluable tumor assessment if they did not receive subsequent anticancer therapy (including on-treatment palliative radiotherapy of non-target bone lesions, skin lesions, or CNS lesions). Subjects who received any subsequent anticancer therapy without a prior reported progression will be censored at the last evaluable tumor assessment before or on the date of initiation of the subsequent anticancer therapy.

All hypotheses testing will be one-sided based on a significance level of 0.025 based on the mITT population.

The distribution of PFS will be compared in the unesbulin and placebo groups via a log-rank test. For subjects with 1 to 3 prior lines of systemic therapy, this will be stratified by prior lines of therapy (1 versus >1), ECOG PS score (0 versus 1), and LMS origin (uterine versus nonuterine). For subjects with at least 4 prior lines of systemic therapy, this will be stratified by ECOG PS score (0 versus 1) and LMS origin (uterine versus nonuterine). The hazard ratio and the corresponding 95% CI will be estimated in a stratified Cox proportional hazards model using randomized group as the single covariate. The PFS curves for each randomized group will be estimated using the Kaplan-Meier (KM) product-limit method. Two-sided, 95% CIs for median PFS will be computed by Brookmeyer and Crowley method (using log-log transformation). PFS rates at 3, 6, 12, 18, 24, and 30 months will also be estimated using KM estimates on the PFS curve for each randomized group. Associated two-sided 95% CIs will be calculated using the Greenwood formula.

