3.2. Estimands

3.2.1. Estimand for Primary Efficacy Analysis (PFS)

Research Question: How does progression free survival time compare between subjects treated with unesbulin (PTC596) in combination with DTIC to those treated with DTIC alone (placebo + DTIC) in the population of subjects with unresectable or metastatic, relapsed or refractory LMS?

Subject Population: Subjects previously treated with 1 to 3 prior lines of systemic therapy, who are randomized to a treatment assignment (unesbulin+DTIC or placebo+DTIC) and further described in the protocol inclusion exclusion criteria.

Endpoint variable: Time from randomization to disease progression or Death due to any cause (whichever occurs first) with disease progression determined according to the RECIST 1.1 and assessed by ICR.

Population-level summary: The hazard ratio (HR) and 95% confidence interval (CI) between unesbulin and placebo

Treatment Condition: unesbulin+DTIC vs. placebo+DTIC

Intercurrent Event Strategy:

- a) Discontinuation of DTIC Treatment Policy
- b) Discontinuation of unesbulin While on treatment
- c) Start of subsequent anticancer treatment: While on treatment

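### SAP Table 3 censors progression or death after a long scan gap, a rule that Protocol 8.4.2 does not contain and SAP 3.7 does not declare

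*SAP*

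**What the plan says.** **Protocol 8.4.2.** The PFS event is progression "determined by the independent, blinded radiologist using RECIST 1.1 or death due to any cause, whichever occurs first". One clear ground for censoring follows: "Subjects who received any subsequent anticancer therapy without a prior reported progression will be censored at the last evaluable tumor assessment". A second sentence, evidently meant for subjects with no event, is garbled: "Subjects who die without a reported prior progress or die will be censored on the date of their last evaluable tumor assessment". Nothing in the section refers to missed scans.

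**SAP 5.1.1 text and SAP 3.2.1.** Both repeat the any-cause definition. In 5.1.1, "PFS is defined as the time from randomization to documented disease progression or death due from any cause, whichever occurs first", and "Subjects who are alive and have not progressed at the time of the analysis will be censored" at the last assessment without progression. The text then refers to Table 3 for the full censoring scheme. The estimand lists three intercurrent events: stopping DTIC, stopping unesbulin, and starting new anticancer treatment. Missed scans are not among them.

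**SAP Table 3.** Progression after a scan gap is censored at the last adequate assessment, and so is death: "If the date of death occurred after missing more than 2 consecutive scheduled scan assessments". The footnote sets the gap at more than 14, 17 or 20 weeks, depending on when the event falls. A death beyond 14 weeks with no post-baseline assessment is censored at randomization.

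**SAP 3.7.** "There are no changes in the protocol-specified analyses of efficacy", whether primary, secondary or exploratory.

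**SAP 5.1.2.** The four sensitivity analyses change the strata, the population, the follow-up cohort or the exposure requirement. None restores an event removed for a scan gap.

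**The concern.** The same death, or the same documented progression, can be a PFS event under the protocol's definition and a censored observation under the SAP. The SAP tells its reader that nothing changed.

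The subjects most exposed are those who stop treatment without progression and are then followed for survival. Protocol Table 1 shows imaging on treatment and at end of treatment, but none in the follow-up columns, while survival calls continue every 3 months. A death can therefore be known long after the last scan. Why a subject stopped may be related to prognosis and may differ by arm, so this censoring may be informative. With no analysis that switches the rule off, a reader of the report could not tell whether it influenced the hazard ratio.

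**Working it through.** **1. The plan's own figures.** Protocol 8.2 sets the interim at 88 of 245 PFS events, with one-sided alpha 0.025 and 2:1 allocation. The information fraction is 88/245 = 0.359. Lan-DeMets O'Brien-Fleming spending is 2[1 − Φ(2.241/√0.359)] = 0.000184, so z = 3.562. The boundary is HR = exp(−3.562/√(88 × 2/9)) = exp(−3.562/4.422) = 0.447. Both stated figures reproduce. They are functions of the event count, so the event definition feeds into them, but no scan-gap rule enters the calculation. (The 245 is not the minimum at HR 0.5. Schoenfeld's formula gives 99 for 90% power, and 245 gives 99.9%. That is a separate matter.)

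**2. The week limits.** Table 3 builds them from two scan intervals plus windows: 6+1+6+1 = 14, 6+1+9+1 = 17, 9+1+9+1 = 20.

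**3. Hypothetical subjects scored both ways.** The gaps in the first two rows exceed all three limits.

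| Subject | Protocol 8.4.2 definition | SAP Table 3 |
|---|---|---|
| Last scan week 10, stops without progression, no new therapy, dies week 32 (gap 22 weeks) | Event, week 32 | Censored, week 10 |
| Stable at week 12, next scan at week 34 shows progression (gap 22 weeks) | Event, week 34 | Censored, week 12 |
| Dosed on day of randomization, no post-baseline scan, dies week 16 | Event, week 16 | Censored at randomization |
| Stable at week 12, dies week 20 (gap 8 weeks) | Event, week 20 | Event, week 20 |
| Stable at week 12, starts new therapy, dies week 20 | Censored, week 12 | Censored, week 12 |

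The first three rows differ. If the garbled protocol sentence is taken literally, the protocol would also censor the deaths in rows 1, 3 and 4. Row 4 would then differ, and row 2 would still differ. The documents disagree on either reading.

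**4. Size by direct range.** Neither document gives a gap frequency. Assume that 2%, 5%, 10% or 15% of events follow a gap:

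- 245 events become about 240, 233, 220 or 208.
- 88 events become about 86, 84, 79 or 75.
- Power = Φ(|ln HR| × √(d × 2/9) − 1.960). At HR 0.5 and d = 208 this is Φ(4.713 − 1.960) = 99.7%, so power at the design effect is not the issue. Because the analyses are event-driven, counting under Table 3 would delay the trigger rather than cut power.
- In a simulation (300 subjects, control median 2 months, 5% or 10% of events in each arm moved back 3.3 to 6 months as censored), the hazard ratio moved by about −0.02 to +0.01. The direction depended on the balance between arms. With no gap events, the two scorings were identical.

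**5. Size by mechanism.** Inputs from Protocol 8.2: 300 subjects, 2:1, 19 months of accrual, 6 further months (cut at month 25), OS medians 10 and 16 months, 11.5% dropout. Assumed: PFS medians 2 and 4 months, dropout taken as stopping without progression, scans at weeks 6, 12, 18 and 24 and then every 9 weeks, a scan at end of treatment and none after it, and every death known.

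| Cut | Share of those stopping who start new therapy | Events removed by Table 3 | HR, protocol definition vs Table 3 |
|---|---|---|---|
| Month 10, about 90 events | 0% | under 1 | – |
| Month 16 | 0% | about 3 | – |
| Month 25 | 0% | about 8 (271 vs 263) | about 0.60 vs 0.57 |
| Month 25 | 50% | 4 | 0.586 vs 0.568 |
| Month 25 | 80% | under 2 | 0.575 vs 0.567 |

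In the largest case the shift is ln(0.60/0.57) = 0.051, against a standard error of about 0.13, or roughly 0.4 standard errors. A repeat run with the same inputs gave matching event counts and a somewhat smaller shift in the hazard ratio, so 0.60 versus 0.57 is best read as the upper end for that setting. If scans continue to progression, the effect is near zero. This model removes deaths only; progressions found after a gap are not sized.

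**The case against.** **The SAP is meant to add detail, and 5.1.1 points to Table 3.** Protocol Section 8 does leave detail to the SAP, and the rule is in plain view, so it is not hidden. But turning an event into a censored observation changes the endpoint, and 3.7 says there is no change. SAP 3.4 also refers to Table 3, but only for subjects without progression or without scans, which does not cover progression found after a gap.

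**The while-on-treatment strategy for stopping unesbulin already covers these subjects.** This has some force, since a death long after stopping fits that strategy poorly as an event. Table 3, however, has no row for stopping unesbulin. Its test is time since the last scan. The link between rule and strategy needs to be stated.

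**Scans continue until progression, so gaps will be rare.** Protocol 7.1 and SAP 1.5 say so, but the visit schedule shows no imaging after end of treatment. The documents leave this open.

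**The trial stopped early.** SAP 3.5 reports a futility recommendation at the interim planned for about 88 events, where the simulated effect is under 1 event. This stands, and the month-25 figures describe a trial run to full accrual.

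Three stronger readings are tempting and not supported:

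- *The protocol counts every progression and death.* It does not. Both documents censor at new anticancer therapy, and the garbled sentence makes even the treatment of deaths unclear.
- *The documents do give different results.* That needs at least one subject with such a gap, and no number is given.
- *The rule was brought in after the interim was seen.* SAP version 1.0 is dated 25 July 2024 and already reports the futility recommendation, although Protocol Section 8 promised a SAP before the interim. But Protocol 3.1 gives the interim its own DMC charter and DMC SAP, which are not among these documents. The date does not show when the rule was devised or which rule the interim used.

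**Conclusion.** The point holds as a discrepancy with a possible effect on the primary result. Table 3 contains a scan-gap rule that Protocol 8.4.2 lacks, the statement in SAP 3.7 is wrong as written, and no planned analysis shows what the rule does. Event counts and the hazard ratio can differ between the documents. Whether they do, and in which direction, depends on gap frequency and arm balance, which are not given.

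On the assumptions above, the effect is negligible near the interim count and modest at full follow-up. The largest shift requires that scans end with treatment, that all deaths are known and that nobody starts new therapy. This should be corrected, but nothing here shows that it would alter the trial's conclusion.

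**What to change.** 1. List the missed-scan rule in SAP 3.7 as a change from the protocol. Align the 3.2.1 estimand with it, including how it relates to the while-on-treatment strategy for stopping unesbulin.
2. Add one sensitivity analysis to SAP 5.1.2. It counts every centrally read progression and every death at its actual date whatever the scan gap, and censors only for no event or new anticancer therapy.
3. Report by arm the number of progressions and deaths that Table 3 censors for a scan gap.
4. Reconcile the Protocol 8.4.2 sentence on subjects who die. It conflicts with the any-cause definition in the same paragraph and with the parallel duration-of-response sentence in 8.4.4, which censors only subjects with neither progression nor death.

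Table 3 may remain the primary analysis. Items 1 to 3 cost SAP wording, one table and one re-run of the PFS program with the gap rule switched off, with no new data. Item 4 is a correction to one protocol sentence. The downside is one more PFS estimate to explain.
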